### Endpoints

The primary endpoint for the XIENCE ISR analysis is target lesion failure (TLFISR). TLFISR is the event rate of the composite outcome of cardiac death, target vessel myocardial infarction (TV-MI) (per primary protocol definition [see Appendix B]), or ischemia-driven target lesion revascularization (ID-TLR), assessed at 1 year.

Non-powered secondary endpoints for the XIENCE ISR analysis to be assessed at 1 year are as follows:

1. Cardiac deathISR
2. TV-MIISR
3. ID-TLRISR
4. Stent thrombosisISR
5. All-cause mortalityISR

In addition, the following outcomes will be reported as sensitivity analyses at 1 year:

6. TV-MIISR,SCAI (periprocedural MI by SCAI definition and spontaneous MI by protocol definition)
7. Periprocedural MIISR,SCAI (by SCAI definition)
8. All MIISR,SCAI (periprocedural MI by SCAI definition and spontaneous MI by protocol definition)
9. TLFISR,SCAI; the composite of cardiac death, TV-MIISR,SCAI or ID-TLR

Note: In the XIENCE ISR analysis population, TV-MIISR and TV-MIISR,SCAI include MI events with confirmed target vessel involvement and indeterminate vessel MI events.

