**Clinical outcomes at 30 days, 1 year and 2 years (unless otherwise noted)**

- 19) Target lesion failure (TLF; cardiac death, TV-MI or ischemia-driven target lesion revascularization (ID-TLR)
- 20) All-cause mortality
- 21) Cardiac and non-cardiac mortality
- 22) All MI
- 23) TV-MI, non-TV-MI and indeterminate vessel MI
- 24) Periprocedural MI and non-periprocedural MI
- 25) All revascularization

- 26) ID-revascularization and non-ID-revascularization
- 27) ID-TVR, ID-TLR, ID-non-TLR TVR, and ID-non-TVR
- 28) Definite, probable and definite/probable stent thrombosis (ARC definition)
- 29) Relationship between immediate post-procedure OCT parameters (e.g. MSA, procedural success, malapposition, dissection, protrusion, etc.) and 2-year endpoint rates (e.g. TVF, TLF, all-cause mortality, cardiac death, TV-MI, all MI, ID-TLR, ID-TVR, and stent thrombosis)
- 30) TVF excluding periprocedural MI (i.e. the composite of cardiac death, target vessel-related spontaneous MI, or ID-TVR) (at 30 days and 1 year)

In addition, the following outcomes using the SCAI definition of periprocedural MI will be reported as sensitivity analyses at 30 days, 1 year and 2 years:

- 31) TV-MISCAI (periprocedural MI by SCAI definition and spontaneous MI by protocol definition)
- 32) Periprocedural MISCAI (by SCAI definition)
- 33) All MISCAI (periprocedural MI by SCAI definition and spontaneous MI by protocol definition)
- 34) TVFSCAI; the composite of cardiac death, TV-MISCAI or ID-TVR

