### **Myocardial Infarction Relation to Target Vessel:**

Infarcts will be adjudicated according to anatomical origin based on review of coronary angiography performed at the time of the event. Those that cannot be clearly attributed to a particular vessel (target or non-target) either because the origin of the event on the angiogram is ambiguous or the angiogram was not performed will be considered as indeterminate vessel MI.

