**Statistical Considerations**

The hypothesis for the XIENCE ISR analysis is as follows:

$H_0$ :  $TLF_{ISR} \geq PG$

$H_a$ :  $TLF_{ISR} < PG$ ,

The null hypothesis will be tested using a one-sided alpha of 2.5%.

For subjects with multiple target vessels,  $TLF_{ISR}$  in any vessel with at least one XIENCE stent implanted on an ISR target lesion constitutes an endpoint event.

The primary endpoint  $TLF_{ISR}$  is assessed to evaluate the safety and effectiveness of XIENCE in ISR lesions. This endpoint must be met to demonstrate success for XIENCE in ISR lesions.

Details on subgroup analyses of the XIENCE ISR primary endpoint  $TLF_{ISR}$  can be found in the separate Statistical Analysis Plan (SAP).

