APPENDIX C: Pre-specified Powered Analysis of XIENCE in the In-Stent Restenosis (ISR) Population

Introduction

Abbott is evaluating the safety and effectiveness of treating in-stent restenosis (ISR) lesions with the XIENCE family of stents within the ILUMIEN IV trial. The trial enrolls patients undergoing planned XIENCE stent implantation during a clinically indicated PCI procedure who satisfy the eligibility criteria described in **Section 5.4** of the CIP. A pre-specified powered analysis of XIENCE is being conducted in randomized ILUMIEN IV subjects with ISR and is described below. The XIENCE ISR analysis is intended to support an indication expansion for treatment of ISR lesions with the XIENCE family of stents in the USA. The XIENCE ISR analysis will be conducted after the last enrolled patient reaches 2 years of follow-up.

The XIENCE ISR analysis is independent of the main ILUMIEN IV study objective outlined in **Section 1.1** of the CIP, which is to demonstrate the superiority of an OCT-guided stent implantation strategy as compared to an angiography-guided stent implantation strategy.

Objective

The objective of the XIENCE ISR analysis is to demonstrate the safety and effectiveness of XIENCE in the treatment of ISR lesions.

Analysis Population

[REDACTED]

Primary Endpoint

The primary endpoint for the XIENCE ISR analysis is target lesion failure (TLF_{ISR}). TLF_{ISR} is the event rate of the composite outcome of cardiac death, target vessel myocardial infarction (TV-MI) (per primary protocol definition in Appendix B), or ischemia-driven target lesion revascularization (ID-TLR), assessed at 1 year. For subjects with multiple target vessels, TLF_{ISR} in any vessel with at least one XIENCE stent implanted on an ISR target lesion constitutes an endpoint event. The primary endpoint TLF_{ISR} is assessed to evaluate the safety and effectiveness of XIENCE in ISR lesions. This endpoint must be met to demonstrate success for XIENCE in ISR lesions.

[REDACTED]

Abbott

Study Name: ILUMIEN IV

Statistical Analysis Plan

Statistical Considerations

The hypothesis for the XIENCE ISR analysis is as follows:

$$H_0: TLF_{ISR} \geq PG$$

$$H_a: TLF_{ISR} < PG$$

where PG (performance goal) equals 20%. The null hypothesis will be tested using a one-sided alpha of 2.5%.

Sample Size and Power

A sample size of 228 subjects will provide approximately 90% power to reject the null hypothesis

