Note: In the XIENCE ISR analysis population, TV-MI_{ISR} and TV-MI_{ISR,SCAI} include MI events with confirmed target vessel involvement and indeterminate vessel MI events

The analysis procedures used for the analysis of the primary endpoint and secondary endpoints for the XIENCE ISR population will be the same as used for the endpoints for the full ILUMIEN IV population as described previously in this SAP.

The XIENCE ISR analysis is independent of the main ILUMIEN IV study objective; therefore, multiplicity adjustment of the primary endpoint TLF_{ISR} is not required.

Additional Analyses to Assess Impact of COVID-19

[REDACTED]

[REDACTED]

[REDACTED]

[REDACTED]

[REDACTED]

[REDACTED]

[REDACTED]

[REDACTED]

[REDACTED]

[REDACTED]

Sensitivity Analyses

Abbott

Study Name: ILUMIEN IV

Statistical Analysis Plan

[REDACTED]

Other Study Considerations

Unless otherwise noted in this appendix, study conduct for the ISR analysis population is the same as for the full ILUMIEN IV population. This consideration applies to risks and benefits, investigator records and reporting, adverse events, clinical data handling, monitoring, compliance, suspension or premature termination of the clinical investigation, ethical considerations, clinical investigation conclusion, publication policy and results reporting on clinicaltrials.gov website.

Abbott

Study Name: ILUMIEN IV

Statistical Analysis Plan

[Redacted text block]

[Redacted text block]

- [Redacted list item]
- [Redacted list item]
- [Redacted list item]
- [Redacted list item]

Abbott

Study Name: ILUMIEN IV

Statistical Analysis Plan

[Redacted content]

Abbott

Study Name: ILUMIEN IV

Statistical Analysis Plan

[Redacted]

[Redacted]

| | | |
|------------|------------|------------|
| [Redacted] | [Redacted] | [Redacted] |
| [Redacted] | [Redacted] | [Redacted] |
| [Redacted] | [Redacted] | [Redacted] |
| [Redacted] | [Redacted] | [Redacted] |
| [Redacted] | [Redacted] | [Redacted] |
| [Redacted] | [Redacted] | [Redacted] |
| [Redacted] | [Redacted] | [Redacted] |
| [Redacted] | [Redacted] | [Redacted] |
| [Redacted] | [Redacted] | [Redacted] |
| [Redacted] | [Redacted] | [Redacted] |
| [Redacted] | [Redacted] | [Redacted] |
| [Redacted] | [Redacted] | [Redacted] |
| [Redacted] | [Redacted] | [Redacted] |
| [Redacted] | [Redacted] | [Redacted] |
| [Redacted] | [Redacted] | [Redacted] |
| [Redacted] | [Redacted] | [Redacted] |
| [Redacted] | [Redacted] | [Redacted] |

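### Read literally, the tested ISR composite TLF_ISR leaves out indeterminate-vessel MI, while its own component TV-MI_ISR and its SCAI version count it; the plan should state one rule.

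*Protocol*

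**What the plan says.** The ISR analysis is described in Protocol Appendix F and SAP Appendix C. Both arms are pooled and the 1-year rate of TLF_ISR is tested against a performance goal.

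- **Primary composite.** Protocol Appendix F (Endpoints) lists cardiac death, "target vessel myocardial infarction (TV-MI) (per primary protocol definition [see Appendix B]), or ischemia-driven target lesion revascularization (ID-TLR), assessed at 1 year". SAP Appendix C has the same components: "target vessel myocardial infarction (TV-MI) (per primary protocol definition in Appendix B), or ischemia-driven target lesion revascularization (ID-TLR), assessed at 1 year". The MI term carries no ISR subscript in either place.
- **Vessel attribution.** Protocol Appendix B, under the heading on MI relation to target vessel, assigns each MI by the angiogram at the time of the event. An MI that is ambiguous on the angiogram, or for which "the angiogram was not performed will be considered as indeterminate vessel MI". Protocol Section 5.3.3 reports the classes side by side: "TV-MI, non-TV-MI and indeterminate vessel MI".
- **The Note.** At the end of the endpoint list in Protocol Appendix F, repeated in SAP Appendix C, TV-MI_ISR and TV-MI_ISR,SCAI are said to "include MI events with confirmed target vessel involvement and indeterminate vessel MI events". TLF_ISR is not named.
- **SCAI version.** TLF_ISR,SCAI is written with the subscripted TV-MI_ISR,SCAI, so the Note reaches it.
- **Several target vessels.** TLF_ISR "in any vessel with at least one XIENCE stent implanted on an ISR target lesion constitutes an endpoint event".
- **Test.** SAP Appendix C gives a 20% goal, one-sided alpha of 2.5%, and 228 subjects for about 90% power.

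**The concern.** The composite that is tested and the component reported beside it appear to follow different rules for the same events. On a literal reading, a subject whose only event is an indeterminate-vessel MI has a TV-MI_ISR event but no TLF_ISR event. The composite would then fail to contain one of its own components.

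The SCAI sensitivity analysis is affected too. It is meant to show what changes when the periprocedural MI definition changes. If TLF_ISR excludes indeterminate-vessel MI and TLF_ISR,SCAI includes it, the comparison changes two things and cannot isolate either.

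The stakes are those of a single pass/fail test meant to support a US indication expansion. The literal reading gives an event count that is equal or lower, and therefore equal or more favourable. A choice of that kind should be fixed in writing before the events are counted.

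**Working it through.** **1. What each term counts, as written.**

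| Term | MI component as written | Indeterminate-vessel MI |
|---|---|---|
| TLF_ISR (tested) | TV-MI, Appendix B definition | not stated; excluded if Appendix B attribution applies |
| TV-MI_ISR | named in the Note | included |
| TV-MI_ISR,SCAI | named in the Note | included |
| TLF_ISR,SCAI | built on TV-MI_ISR,SCAI | included |

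No visible sentence fills the first row directly.

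**2. Decision limit.** Inputs from SAP Appendix C: n = 228, goal 0.20, one-sided alpha 0.025. The test statistic is not visible, so I used the exact binomial and checked it with the score test. All 228 subjects are taken as evaluable at 1 year.

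- 33 events (33/228 = 14.5%): P(X ≤ 33 | 228, 0.20) = 0.0196; 97.5% upper bound 19.7%. Pass.
- 34 events (14.9%): P(X ≤ 34 | 228, 0.20) = 0.0298; 97.5% upper bound 20.2%. Fail.
- Score test, z = (x/228 − 0.20) / √(0.20 × 0.80/228), with denominator 0.0265: −2.09 at 33 and −1.92 at 34, against −1.96. Same limit.

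One reclassified MI at the boundary can therefore change the verdict.

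**3. The stated power.** The planning rate for TLF_ISR is not visible, so the 90% cannot be reproduced from the documents' inputs. Solving P(X ≤ 33 | 228, p) = 0.90 gives p = 0.119, about 27 events. A rate of 12% gives 89.2% exact power and 90.4% by the normal approximation with null variance. The stated power is plausible with a planning rate near 12%.

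**4. How often the two readings disagree.** Let d be the proportion of subjects whose only qualifying event is an indeterminate-vessel MI. The broad count is never below the narrow count, so the readings disagree only when the narrow count passes and the broad one fails. With the same denominator,

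P(disagree) = P(X ≤ 33 | narrow rate) − P(X ≤ 33 | broad rate).

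The documents do not give d, so its values are assumed. Nor do they show whether the unseen planning rate already includes these MIs, so both cases are given.

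| d (subjects of 228) | 11.9% excludes them: narrow / broad power | Disagree | 11.9% includes them: narrow / broad power | Disagree |
|---|---|---|---|---|
| 0.5 points (1.1) | 90.0% / 85.2% | 4.8% | 93.6% / 90.0% | 3.6% |
| 1 point (2.3) | 90.0% / 79.1% | 10.9% | 96.2% / 90.0% | 6.2% |
| 2 points (4.6) | 90.0% / 64.1% | 25.9% | 98.9% / 90.0% | 8.9% |

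For d of 0.5 to 1 point the range is roughly 4% to 11%. The 2-point row is an extreme illustration: it needs 4.6 further subjects on top of about 27, or 17% more (4.6/27), with no other event.

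**The case against.** The strongest reply is that this is loose notation. In Protocol Appendix F every component of TLF_ISR is written without a subscript, including cardiac death and ID-TLR, yet all three appear with the subscript in the secondary list. The SCAI composite mixes both styles in one line. The subscript may do no more than label the population. The Note opens by referring to the ISR analysis population and closes the section that defines TLF_ISR, so one rule throughout may be intended. The reference to the primary protocol definition matches the Appendix B heading for the MI biomarker and ischaemia criteria, as opposed to SCAI; vessel attribution sits under a different heading. In addition, SAP text directly after the primary endpoint paragraph is redacted and SAP Appendix B is not visible. Either could settle the matter.

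All of this stands as a reason not to call the plan contradictory. It does not show which reading applies. The Note names two terms and omits the tested one, and the Protocol appendix would have to agree with whatever the redacted SAP text says.

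A reader might also infer three stronger points that the documents do not support:

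- **The tested count has two defined values.** It has one literal definition and one plausible intended definition.
- **The several-vessels sentence rules out indeterminate-vessel MI.** It cannot demand vessel attribution of every component, because cardiac death belongs to no vessel. It also concerns only subjects with more than one target vessel.
- **The verdict is at risk in about a quarter of cases.** That figure needs the 2-point assumption and a planning rate that excludes these MIs. Nothing in the documents supports the first, and nothing visible establishes the second. Since attribution rests on an angiogram at the time of the event, periprocedural MIs should seldom be indeterminate.

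**Conclusion.** The point holds as a mismatch in the stated rules. The protocol text read literally leaves indeterminate-vessel MI out of the tested composite while its component and its SCAI version count it, and no visible sentence resolves this. The loss of a clean SCAI comparison follows on the same literal reading only.

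The limit of 33 events rests on figures in the SAP and is firm for 228 evaluable subjects. The 4% to 11% chance of opposite verdicts is conditional on an assumed 0.5 to 1 point of subjects whose only event is an indeterminate-vessel MI, and on a planning rate near 12% back-solved from the stated power. The true effect may be smaller. No stated figure is shown to be wrong, and the main TVF endpoint is not in question. I would label this a cheap improvement.

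**What to change.** In Protocol Appendix F and SAP Appendix C:

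1. Write the MI component of TLF_ISR as TV-MI_ISR, meaning the primary protocol MI definition with indeterminate-vessel MI included. The composite, its component and TLF_ISR,SCAI then share one vessel rule.
2. In the sentence on subjects with several target vessels, add that an indeterminate-vessel MI counts as a TLF_ISR event.
3. Report TLF_ISR without indeterminate-vessel MI as a sensitivity analysis, unless the redacted sensitivity section already does so.

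The inclusive form follows the sponsor's own Note and is the conservative choice for a test against a goal. If redacted SAP text already states it, only the Protocol wording needs to be aligned. The cost is a few words in each document and possibly a slightly less favourable TLF_ISR rate. No new data are needed, because Appendix B already has these MIs adjudicated as a class. The edit should be made before ISR events are counted.

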### Procedures

The procedures for the ISR analysis population are the same as for the full ILUMIEN IV population.

**Statistical Considerations**

The hypothesis for the XIENCE ISR analysis is as follows:

$H_0$ :  $TLF_{ISR} \geq PG$

$H_a$ :  $TLF_{ISR} < PG$ ,

The null hypothesis will be tested using a one-sided alpha of 2.5%.

For subjects with multiple target vessels,  $TLF_{ISR}$  in any vessel with at least one XIENCE stent implanted on an ISR target lesion constitutes an endpoint event.

The primary endpoint  $TLF_{ISR}$  is assessed to evaluate the safety and effectiveness of XIENCE in ISR lesions. This endpoint must be met to demonstrate success for XIENCE in ISR lesions.

Details on subgroup analyses of the XIENCE ISR primary endpoint  $TLF_{ISR}$  can be found in the separate Statistical Analysis Plan (SAP).

**Other Study Considerations**

Unless otherwise noted in this appendix, study conduct for the ISR analysis population is the same as for the full ILUMIEN IV population. This consideration applies to risks and benefits, investigator records and reporting, adverse events, clinical data handling, monitoring, compliance, suspension or premature termination of the clinical investigation, ethical considerations, clinical investigation conclusion, publication policy and results reporting on clinicaltrials.gov website.

1.0 INTRODUCTION

This document is a statistical analysis plan for the ILUMIEN IV trial (refer to ABT-CIP-10233 for the clinical investigational plan).

2.0 TRIAL OBJECTIVES

The objective of this clinical investigation is to demonstrate the superiority of an Optical Coherence Tomography (OCT)-guided stent implantation strategy as compared to an angiography-guided stent implantation strategy in achieving larger post-PCI lumen dimensions and improving clinical cardiovascular outcomes in patients with high-risk clinical characteristics and/or with high-risk angiographic lesions. In addition, embedded within the ILUMIEN IV protocol is a separate pre-specified powered analysis of XIENCE to be conducted in randomized ILUMIEN IV subjects with in-stent restenosis (ISR). The objective of the analysis is to demonstrate the safety and effectiveness of XIENCE in the treatment of ISR lesions. This is described in further detail in Appendix C.

3.0 TRIAL DESIGN

This is a prospective, single-blind clinical investigation randomizing subjects to OCT-guided coronary stent implantation vs. angiography-guided coronary stent implantation in a 1:1 ratio. The clinical investigation will be conducted at approximately 125 centers in North America (US and Canada), Western Europe, and Asia-Pacific. Up to 3656 randomized subjects and approximately 375 roll-in subjects will be enrolled in the clinical investigation. No site may enroll more than 15% of the total subjects. Subjects participating in this clinical investigation will be followed for 2 years. The expected duration of enrollment is approximately 2 years. The total duration of the clinical investigation is expected to be approximately 5 years.

The sample size is driven by the primary endpoint of target vessel failure (TVF). Because of the event driven nature of this primary endpoint, the statistical power of the trial is a function of the number of endpoint events, and not a direct function of the number of patients enrolled. As a result, the number of patients is not an endorsement of the statistical power of the trial. If event rates are lower than anticipated, more patients will be required to obtain a sufficient number of endpoint events.

Subjects will be randomized in a 1:1 ratio according to an electronic randomization system. Randomization will be stratified by medically treated diabetes, presentation with a biomarker positive ACS (NSTEMI or recent STEMI), and site.

Each operator will complete OCT-guided stenting roll-in cases (up to 3, if needed) according to a pre-specified stent optimization protocol on patients meeting study inclusion/exclusion criteria. Within 72 hours of receipt, the core lab will determine accurate OCT measurements and stent optimization protocol compliance. OCT Core laboratory approval of each operator is required to proceed to the randomization phase.

Subjects will be considered enrolled in the trial once informed consent has been obtained and the subject is randomized. The trial will utilize a Clinical Events Committee (CEC) to review adverse events for adjudication of trial endpoints.

4.0 TRIAL ENDPOINTS

There are two powered primary endpoints, one powered major secondary endpoint and multiple descriptive non-powered secondary endpoints in this clinical investigation.

4.1 Primary Endpoints

4.1.1 Imaging Outcome (powered): Minimal Stent Area (MSA), continuous measure

The primary imaging endpoint is Final Post-PCI MSA (per target lesion basis) in each randomized arm, as measured at an independent OCT core laboratory, which is blinded to imaging modality assignment.

4.1.2 Clinical outcome (powered): Target Vessel Failure (TVF)

The primary clinical endpoint is the time-to-first event rate of the composite outcome of cardiac death, target vessel myocardial infarction (TV-MI) (per primary protocol definition), or ischemia-driven target vessel revascularization (ID-TVR) assessed at 2 years.

Testing between OCT and angiography will be done in a hierarchical manner as follows:

1. Superiority of MSA in OCT-guided arm vs. Angiography-guided arm
2. Superiority of TVF in OCT-guided arm vs. Angiography-guided arm

4.2 Major Secondary Endpoint

4.2.1 Target vessel failure (TVF) excluding periprocedural MI

The major secondary endpoint is time-to-first event rate of the composite outcome of cardiac death, target vessel-related spontaneous myocardial infarction, or ischemia-driven target vessel revascularization (ID-TVR), assessed at 2 years.

4.3 Non-Powered Secondary Endpoints

The trial has a number of non-powered secondary endpoints such as procedural outcomes, additional procedural and clinical endpoints, patient reported outcomes (PRO) and cost-effectiveness measures. See Section 5.4 for a full listing.

5.0 STATISTICAL METHODS

5.1 Analysis Populations

5.1.1 Intent-to-Treat (ITT) Population

[REDACTED]

